# 6.2 Subject Exclusion Criteria

- 1. Pregnant or breast-feeding
- 2. Have had chemotherapy (including purine analogs, rituximab, and other investigational agents) within six weeks prior to entering the study
- 3. Major surgery within 4 weeks prior to entering the study
- 4. Invasive malignancy within the past 2 years prior to first study drug administration, except for adequately treated (with curative intent) basal or squamous cell carcinoma, melanoma, in situ carcinoma of the cervix, in situ ductal adenocarcinoma of the breast, in situ prostate cancer, or limited stage bladder cancer or other cancers from which the patient has been disease-free for at least 2 years
- 5. Refractory nausea or vomiting, malabsorption, external biliary shunt, or history of any type of gastrointestinal surgery that would preclude adequate absorption of study drug
- 6. Prior treatment with MEK or BRAF inhibitors
- 7. Active HIV, hepatitis B and hepatitis C
- 8. Patients with HCL variant (as defined by absence of expression of CD25 or absence of BRAF V600E mutation)

# 7.0 RECRUITMENT PLAN

Potential research subjects will be identified by a member of the patient's treatment team, the protocol investigator, or research team at Memorial Sloan-Kettering Cancer Center (MSKCC). Patient recruitment will occur in medical oncology clinics or the inpatient service of the Leukemia Service at MSKCC. Investigators will screen the patient's medical records of suitable research study participants and discuss the study and their potential for enrolling in the research study. Similar recruitment procedures will be followed at collaborating institutions. It is expected that each of the participating sites will enroll 5-7 patients each over a 2-year period.

Participating site recruitment will be conducted as outlined within the protocol. Any participating sites that require a limited waiver must obtain it from their site IRB/PB via a separate protocol addendum or request. It is the responsibility of the MSK staff to confirm participating data collection sites have a limited waiver approved by their local IRB(s)/PBs.

# 8.0 PRETREATMENT EVALUATION

The following assessments must be performed prior to treatment start:

#### Within 4 Weeks of Study Start:

- A complete history and physical exam including general ophthalmologic examination for any signs of conjunctiva inflammation and regular constrictions of pupils
- Head and neck examination: visual inspection of the oral mucosa and lymph node palpation
- ECG
- Laboratory studies: CBC with differential and platelets, smear review, Comprehensive Metabolic Panel (albumin, alkaline phosphatase, total bilirubin, bicarbonate, BUN, calcium, chloride, creatinine, glucose, potassium, total protein, SGOT [AST], SGPT [ALT], and sodium), phosphorus, uric acid, LDH, PT/PTT, HIV, Hepatitis B and C testing
- CT chest
- CT abdomen in patients with intact spleen
- Bone marrow aspirate for histology, cytogenetics, immunophenotyping by flow cytometry, and a bone marrow biopsy. If bone marrow aspirate cannot be obtained, peripheral blood samples will be tested for cytogenetics and immunophenotyping by flow cytometry.
- Full skin assessment by a dermatologist or equivalent trained skin cancer expert
- Research blood or bone marrow aspirate (if obtained) analysis (please see Section 10.3 for details of the study)

# Within 7 Days of Study Start:

Serum pregnancy test for women of child-bearing potential

# 9.0 TREATMENT/INTERVENTION PLAN

#### 9.1 Administration of Vemurafenib

Patients will receive vemurafenib at a dose of 960mg orally b.i.d. continuously in cycles of 4 weeks (28 days) as outpatient. A bone marrow aspirate and/or biopsy will be performed after the first cycle for research purposes only. After the completion of the third cycle, a repeat bone marrow aspirate and/or biopsy will be performed for assessment of response and evaluation of MRD. Following the third cycle assessments, patients who achieve complete response (CR) with detectable MRD or partial response (PR) may continue with vemurafenib for up to 3 additional cycles at the treating physician's discretion (Cycles 4-6). Patients who achieve CR without MRD will be observed as part of post-treatment followup, and may be re-treated with vemurafenib after relapse (as per below). Patients who achieve no response (NR) after the initial 3 cycles of vemurafenib will be removed from the study.

After patients discontinue vemurafenib, they will be followed every 3 months as part of post-treatment followup for a total of 12 months. Patients who previously experienced CR, PR (either hematologic or MRD) or clinical benefit, but who subsequently relapse after ending treatment may be retreated with Vemurafenib until disease progression or at the treating physician's discretion. Patients who are re-treated will follow the treatment/evaluation plan as outlined in Table 3 (see Section 10). A bone marrow aspirate and/or biopsy may be performed for assessment of response at the end of the third re-treatment cycle or during a subsequent re-treatment cycle when clinically indicated.

Patients who achieve no response after the initial 3 cycles of vemurafenib will be removed from the study. In case of certain defined toxicities, dose reductions by 50% (480mg b.i.d.) or interruptions of up to 15 days are permitted. If additional dose reductions are required, vemurafenib may be reduced to 240mg oral b.i.d.

#### 9.2 Dose Modifications

Management of Symptomatic Drug Reactions: Symptomatic drug reactions (e.g. arthralgia, fatigue, rash) may require temporary interruptions and/or dose reduction of vemurafenib treatment. Arthralgia is one of the common side effects of the drug, and can be first managed with prednisone 5-10mg daily before dose reduction is attempted. When dose reduction is needed, initial dose reduction to 480mg b.i.d. is recommended based on individual safety and tolerability data from the trials in melanoma patients. If additional dose reduction is required or the drug is interrupted for up to 15 days, vemurafenib may be reduced to 240mg b.i.d. Dose escalation after dose reduction is generally not recommended unless under special circumstances (i.e. increased likelihood of clinical benefit for the dose increase and no safety concern). This should be done after discussion with the the principal investigator of the study ([name]). Dose increase above 960mg b.i.d. will NOT be allowed.

**Management of QT**c **Prolongation:** Special consideration must be taken with any patient on study with an increase in QTC >500ms or change from baseline >60ms. If QTC exceeds 500 ms or the change from baseline is > 60ms on ECG (measured in triplicate), vemurafenib treatment should be temporarily interrupted. When QTC decreases to < 500ms, re-initiation of vemurafenib treatment may occur and patients should be dose reduced by one dose level. Permanent discontinuation of vemurafenib treatment is recommended if QTC increase meets both criteria of >500ms and >60ms change from pre-treatment values of if QTC >500ms or change from baseline >60ms is observed on 2 prior independent occurrences.

**Management of Grade 1-4 Non-Hematologic Toxicities:** For any grade 1 and tolerable grade 2-3 toxicities, patients may continue full dose. For any intolerable grade 2-3 toxicities, dosing will be interrupted until resolution to grade 1 or less and dose reductions to 480mg b.i.d. are required, except for arthralgia in which case prednisone 5-10mg daily can be attempted first before the study drug dose reduction. If additional dose reduction is required, investigators can further reduce the dose to 240mg b.i.d. On the third appearance of any grade 2 or grade 3 adverse events despite two dose reductions, it is recommended that patients discontinue vemurafenib. For any grade 4 toxicities, patients should discontinue study treatment or, based on investigator judgment, interrupt until resolution to grade 1 or less with dose reduction to 240mg b.i.d. upon restarting study drug. Dose escalation after dose reduction is generally not recommended unless under special circumstances (i.e. increased likelihood of clinical benefit for the dose increase and no safety concern). It is recommended that patients permanently discontinue vemurafenib for a second occurrence of any grade 4 toxicities.

**Prolonged Drug Interruptions:** If a patient's study dose has been interrupted for >15 days, the patient will be considered to have discontinued from the study. If the patient is still benefiting from treatment and an interruption greater than 15 days deemed necessary by the investigator, the length of the requested interruption should be discussed with the principal investigator of the study ([name]). Restarting vemurafenib treatment after discontinuation of drug is permitted during the re-treatment phase if the investigator deems there is a clinical benefit for re-starting drug and there are no safety concerns.

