# 11.10 Cardiac Toxicity

Data from the phase II trial indicate that some patients treated with vemurafenib 960mg twice a day developed mild QTc prolongation. The largest mean QTc change from baseline was 15.1 milliseconds (msec). One patient on study had a QTc change of >60 msec. Two patients (1.5%) developed QTc prolongation >500 msec. No ventricular arrhythmias have been reported to date.

The following recommendations have been developed to minimize the risk of arrhythmias on study:

- Avoid combination with other agents with known potential to lead to QTc prolongation.
- ECG should be monitored on day 1 prior to the first dose of vemurafenib, pre-dose on day 15 after study drug initiation, every 4 weeks for the next 3 cycles, and every 12 weeks thereafter.
- o If QTc interval exceeds 500 msec or the change from baseline is >60 msec, on three separate ECGs, vemurafenib treatment should be temporarily interrupted. The investigator should check electrolytes (K, Mg, and Ca), correct any electrolyte abnormalities prior of reinstitution of therapy, recheck concomitant medications to insure that non has been implicated in QTc prolongation, and rule out or control other cardiac risk factors (i.e. ischemia). Monitor ECG weekly until QTc decreases to < 500 msec and reinitiate treatment at once reduced level from 960 mg b.i.d. to 480 mg b.i.d.

- Vemurafenib should be permanently discontinued if a QTc increase meets both criteria of > 500 msec and > 60 msec change from pre-treatment values or if QTc > 500 msec or change from baseline > 60 msec is observed on two separate occasions.

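### For QTc events meeting one criterion only, Sections 9.2 and 11.10 appear to stop drug at different episodes, and the restart threshold in both is already met when a change-only event interrupts drug

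*Combined protocol and SAP*

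**What the plan says.** **Section 9.2 (Management of QTc Prolongation).** It opens "Special consideration must be taken with any patient on study with an increase in" QTc above 500 ms or a change from baseline above 60 ms. Either finding, on ECGs in triplicate, interrupts drug. Once QTc is below 500 ms, "re-initiation of vemurafenib treatment may occur and patients should be dose reduced by one dose level". Permanent discontinuation is recommended when both criteria are met together, or when QTc above 500 ms or a "change from baseline >60ms is observed on 2 prior independent occurrences".

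**Section 11.10 (Cardiac Toxicity).** The triggers are the same, on three separate ECGs. Before restart the investigator is to check electrolytes and "correct any electrolyte abnormalities prior of reinstitution of therapy", recheck concomitant medications, and "rule out or control other cardiac risk factors". The ECG instruction is "Monitor ECG weekly until QTc decreases to < 500 msec", and then to "reinitiate treatment at once reduced level from 960 mg b.i.d. to 480 mg b.i.d". Drug should be stopped permanently when both criteria are met, or when QTc above 500 ms or a "change from baseline > 60 msec is observed on two separate occasions".

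Section 11.1 refers readers to Section 9.2 for toxicity management in general. No text says which QTc rule prevails if the two differ.

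**The concern.** The point covers only events that meet one criterion. Events meeting both lead to permanent discontinuation in both sections.

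There are two separate problems. First, the sections appear to count differently before stopping. A site working from Section 9.2 alone could restart at 240 mg b.i.d. after a second episode, where Section 11.10 says to stop. Second, and however the count is read, the restart threshold does no work when the trigger was the change from baseline. The interruption can end, and the weekly ECGs with it, while the change that caused the interruption is still present.

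The two problems also interact. If the first change need not resolve, a later ECG still above 60 ms could be taken as the same episode or as a new one, and the stopping count depends on which.

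**Working it through.** **1. Stopping count, side by side (single-criterion events)**

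| Episode | Section 9.2, natural reading | Section 11.10 |
|---|---|---|
| 1 | interrupt, restart at 480 mg b.i.d. | interrupt, restart at 480 mg b.i.d. |
| 2 | interrupt, restart at 240 mg b.i.d. | stop |
| 3 | stop | – |

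The Section 9.2 column takes the word prior at face value: two earlier episodes, then the current one. Two features fit this reading. Section 9.2 reduces by one level at a time and has two levels below 960 mg. Its neighbouring rule for grade 2 or 3 toxicity also stops at the third appearance, after two reductions. Section 11.10 names a single step, 960 to 480 mg.

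**2. Restart threshold**

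Let b be baseline QTc (below 480 ms by inclusion criterion 6) and q the on-treatment QTc.

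- Change-only event: q − b > 60 and q ≤ 500, which requires b < 440. The restart condition q < 500 already holds unless q = 500.
- Event above 500 ms only: q > 500 and q − b ≤ 60, which requires b > 440. Here q < 500 is not yet met, so the threshold works as intended.

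A count over whole-millisecond values (b from 340 to 479, q from b to 600) confirms this:

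- Change-only: 5,050 combinations. The restart condition is already met in 4,950; the other 100 all have q = 500.
- Above 500 ms only: 780 combinations. The restart condition is already met in none.

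Example: b = 400 and q = 465 give a change of 65 ms. Drug is interrupted, and 465 is already below 500.

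**3. How often this could arise**

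Inputs: Section 11.10 reports, from the phase II trial, two patients (1.5%) with QTc above 500 ms and one with a change above 60 ms. Section 11.4 gives 132 patients for the phase 2 melanoma study. The plan's percentage is reproduced by 2/132 = 1.5%, which supports taking 132 as the denominator.

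The documents do not say whether the patient with the change above 60 ms was also one of the two above 500 ms, so a range is needed.

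- Single-criterion first events, lower end (that patient is one of the two and met both criteria in the same event, so is excluded): 1/132 = 0.0076.
- Single-criterion first events, upper end (no overlap): 3/132 = 0.0227.
- Expected in 36 patients: 36 × 1/132 = 0.27 to 36 × 3/132 = 0.82.
- Chance of at least one: 1 − (131/132)^36 = 24% to 1 − (129/132)^36 = 56%.
- Change-only events (restart problem): 0 to 1/132, so 0 to 0.27 expected and a 0% to 24% chance of at least one.
- Second episodes (count problem): the documents give no recurrence rate. Assuming 25% to 50% recur after restart gives 0.27 × 0.25 = 0.07 to 0.82 × 0.50 = 0.41 expected.

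**The case against.** The case against the count is that both sections use the number two, and Section 9.2 can be read as counting episodes already observed. Where Section 9.2 means a third event it says so, in the grade 2 or 3 rule; its grade 4 rule stops at a second occurrence, so the section contains both patterns. Stopping at the second episode breaches neither section, because Section 9.2 is worded as a recommendation. This objection stands to the extent that the split is the natural reading and not a proven contradiction. It does not remove the ambiguity: restarting after a second episode is consistent with Section 9.2 as it reads and contrary to Section 11.10.

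On restart, Section 9.2 is permissive, the dose is always reduced, and the Section 11.10 checks apply. ECGs also continue after the weekly ones end: every 4 weeks for the next three cycles, then every 12 weeks, with ECGs in re-treatment too. QT prolongation is an adverse event of special interest, and monthly all-site calls review toxicity. These safeguards reduce the risk. None of them requires the change to resolve before drug restarts, and scheduled ECGs can be about three months apart late in re-treatment.

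The documents do not establish that a change of at most 60 ms is the right clinical standard for restart. The argument is one of internal consistency: the protocol treats a larger change as enough to interrupt drug, and for intolerable grade 2 or 3 toxicity it ties restart to recovery to grade 1 or less.

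The frequency figures use all 36 patients from first dose, and so do not measure how many patients an amendment would reach now. They also rest on two or three melanoma patients and allow for overlap between them, not for sampling error. Both criticisms are fair.

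**Conclusion.** The concern holds as a minor point of patient-safety wording.

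The restart gap is the firmer half. It follows from the two thresholds and does not depend on how the stopping rule is read. The count divergence rests on reading prior in its ordinary sense; if that word is loose drafting, the sections agree.

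Across 36 patients the expected numbers are 0.27 to 0.82 single-criterion first events, 0 to 0.27 change-only events, and 0.07 to 0.41 second episodes. These assume that the phase II QTc data come from the 132-patient study, that melanoma rates carry over to hairy cell leukemia, and, for second episodes, a 25% to 50% recurrence rate.

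Present reach is smaller. Accrual closed in August 2016 and initial treatment is limited to six cycles, so only patients still on treatment or re-treatment are affected. The documents do not give their number. The primary endpoint, sample size and analysis are untouched.

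**What to change.** - **One count.** State in both sections that drug is permanently discontinued at the second separate single-criterion episode. This is the Section 11.10 rule, and it also satisfies Section 9.2.
- **One restart rule.** In both sections require QTc below 500 ms **and** a change from baseline of at most 60 ms before restart at the reduced dose, with weekly ECGs until both are met.
- **A cross-reference.** Point Section 9.2 to the electrolyte, concomitant-medication and cardiac-risk checks in Section 11.10.

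The cost is a wording amendment and a memo to sites. A few patients may stop permanently one episode earlier. Some change-only interruptions will last longer and could reach the 15-day limit in Section 9.2, beyond which the length has to be discussed with the principal investigator.

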# 10.0 EVALUATION DURING TREATMENT/INTERVENTION

#### 10.1 Clinic Visits

Outpatient clinic visits will occur weekly during the Cycle 1 (Days 1, 8, 15, 22), and on Day 1 of subsequent 28-day cycle (*i.e.* monthly, days 29, 57, 85, etc.). A +/- 4 day window will be allowed for completion of scheduled clinic visits. Please refer to the **Table 1** below for details of routine tests to be performed during the clinic visits. As specified in **Table 1**, some of the blood tests and assessments can be obtained locally if the patient has an established local oncologist.

# 10.2 Disease Response Assessment

Disease response assessment will be performed after the completion of Cycle 3, and will involve CBC with diff and platelets, a bone marrow aspirate and/or biopsy (flow cytometry, cytogenetics, IHC), and CT Abdomen (CT Abdomen is applicable only if splenomegaly was present on screening the CT abdomen). MRD analysis will be performed on bone marrow biopsy specimens as assessed by IHC for anti-CD20, DBA 44 and anti-CD45RO. If patients receive additional cycles of therapy (*i.e.* Cycles 4, 5 and 6), the above disease response assessment will occur within 2 weeks of the last therapy.

#### 10.3 Research Tests

The following research tests will be performed at the time points indicated in **Table 1**. Bone marrow aspirate samples will be collected in an EDTA-containing syringe (3-5ml) and peripheral blood samples will be collected in either green top or purple top tubes (10ml). At each specified time point (Table 1), 3 green or purple top tubes of peripheral blood samples will be collected. These samples can be collected locally if the patient has an established local oncologist and only after discussing with the study PI. The collected samples will be delivered to the [name]'s laboratory in [name] at Memorial Sloan-Kettering Cancer Center.

**BRAF Mutation Analysis:** Peripheral blood and/or bone marrow aspirate samples from pretreatment and post-treatment at specified time points will be assessed for BRAF V600E mutation by allele-specific PCR of genomic DNA followed by conventional agarose-gel electrophoresis and/or by quantitative real-time allele-specific PCR in complimentary DNA (cDNA).

Pharmacodynamic (PD) Studies: Peripheral blood and/or bone marrow aspirate samples from pre-treatment and post-treatment at specified time points will be assessed by Western Blot or by phospho-flow for the downstream targets of BRAF (MEK, pMEK, ERK, pERK) to assess the on-target effect of the Vemurafenib. In addition, signaling studies using Cell Biosciences NanoPro 1000 technology will be performed on the same samples, which will allow us to obtain accurate, quantitative signaling on the entire MAPK, PI3K, and JAK-STAT pathways before and after treatment on sorted circulating hairy cells.

\*For MSKCC Patients ONLY: Additional research blood samples for the above mentioned pharmacodynamic studies will be collected in patients who receive their treatment at MSKCC. These additional time points include 2-4 hours and 24 hours after the first dose of vemurafenib. 24-hour blood sample can be collected locally if the patient has an established local oncologist and only after discussing with the MSKCC PI.

Molecular Characterization of HCL: Peripheral blood and/or bone marrow aspirate samples from pre-treatment and post-treatment at specified time points will be analyzed by high throughput next generation sequencing using the Raindance multiplex PCR platform and Illumina next generation sequencing to perform comprehensive mutation profiling for BRAF and for 29 additional genes known to be mutated in HCL patient and/or in other chronic B-cell lymphoid malignancies.

Biomarkers for Resistance: The following tests will be performed in all patients at baseline, and in patients who do not achieve CR or PR after completing 3 cycles of therapy, or who progresses after achieving CR or PR.

- Reactivation of MAPK pathways: Increased expression of the other RAF isoforms CRAF and ARAF), and MAPK (MAPK8 or COT) will be analyzed by Western Blot and/or real-time PCR.
- Secondary BRAF mutations (all 18 BRAF exons) and RAS mutations will be analyzed by bi-directional Sanger sequencing and by Raindance multiplex PCR and Illumina next generation sequencing, respectively.
- Activation of RTKs (i.e. PDGFRβ and IGF-IR) will be assessed by Western Blot.
- Cell Biosciences NanoPro 1000 technology will be used to examine quantitative signaling on the entire MAPK, PI3K and JAK-STAT pathways.

**Table 1: Evaluation on Study** 

Phase	Screening	Study Visits											
Cycle		1		2		3	4 5			6			
Day 	-28 to -1	Day 1	Day 8	Day 15	Day 22	Day 1	Day 15	Day 1	Day 28+/-4	Day 1 	Day 1	Day 1	Day 28+/-4
Informed Consent	X												
History and Physical Exam	X	X				X		X		X	X	X	
Head and Neck Exam 	X	X				X					X		
ECG	X	X		X12		X		X		X			
Serum Pregnancy Test 	X												
Dermatology Exam 	X					X					X		
CBC w/ diff, Platelets	X	X	X12	X12	X12	X	X 	X	X	X	X	X	X
Smear Review	X	X	X12	X12	X12	X		X		X	X	X	
COMP, LDH	X	X				X		X	X	X	X	X	X
Phosphorus, Uric Acid	X	X	X 	X 	X 								
PT/PTT	X												
HIV, Hepatitis B and C	X												
Adverse Events		X				X		X		X	X	X	
Review of Concomitant Medications	X	X				X		X		X	X	X	
CT Chest	X								X 				
CT Abdomen	$X^6$								X 				
Bone Marrow Aspirate and/or Biopsy	X								X				$X^8$
Research Tests													
Bone Marrow Aspirate and/or Biopsy	X 					X 			X 				X 
Peripheral Blood 	X	X 	X 	X 	X 	X		X	X	10.0			X8

<sup>1A +/- 4 day window will be allowed for completion of scheduled clinic visits (i.e. holidays, travel delays, site closures, other reasons, etc.) A +/- 7day window is allowed for Cycle 4 Day 1 to allow the adequate time for bone marrow response evaluation from Cycle 3 Day 28.

<sup>2Head and neck examination can be performed as part of general physical exam, and consist of visual inspection of the oral mucosa and lymph node palpation.21

<sup>3In women of child-bearing potential, serum pregnancy test should be obtained within 7 days prior to start of treatment.

<sup>4A window of +/- 21 days of scheduled visit (with exception of screening) is allowed for completion of these assessments.

<sup>5CT chest at Cycle 3, Day 28 will be performed if considered clinically indicated at the discretion of treating physicians (e.g. monitoring infection or pulmonary nodules).

<sup>6CT abdomen at screening will be performed if patient has intact spleen.

<sup>7CT abdomen at Cycle 3, Day 28 will be performed if splenomegaly present on screening CT abdomen.

<sup>8Only for those who continue vemurafenib for > 3 cycles.

<sup>93-5ml of bone marrow aspirate will be collected in an EDTA-containing syringe.

<sup>103 green or purple top tubes (10cc tubes) will be collected for all patients at the specified time-points.

<sup>11For MSKCC patients only, 3 green/purple top tubes will be collected at 2-4 hours and 24 hours after the first dose of vemurafenib. For patients treated at other centers, only the pre-treatment blood samples will be drawn (3 green top tubes).

<sup>12 This test may be done locally

Cycle 3 Day 28 visit may serve as Cycle 4 Day 1 visit for patients who will continue beyond 3 cycles for high suspicion of residual disease before waiting for BMB result at the treating phsyicain's discretion.

Table 2: Procedures for End of Treatment and Post Treatment Follow Up Visits

Phase	End of Treatment	Post Treatment Follow-Up 
Time Frame	4 weeks from last treatment dose	Every 3 months post last dose
History and Physical Exam	X	X
Head and Neck Examination		X
Dermatology Evaluation 	X	X
CBC w/ diff & Platelets, COMP, LDH	X	X
Survival assessments 	X	X

<sup>1These evaluations will continue up to 12 months after study drug discontinuation.

